**3.2.3 Follow-up 1 visit**

*Subjects should attend wearing the study lenses which should have been in situ for at least two hours. Subjects who attend without lenses in situ for at least two hours will usually be rescheduled. The following procedures will be performed (any ocular measurement procedures outlined below will be carried out on each eye):*

1. Any medical or ocular issues since the last visit will be recorded.
2. [REDACTED]
3. [REDACTED]
4. [REDACTED]
5. [REDACTED]  
[REDACTED]  
[REDACTED]  
[REDACTED]  
[REDACTED]
6. The subject will be asked to score the following with reference to appropriate vertical visual analogue scales (0-100) [REDACTED]
  - Comfort after insertion
  - Comfort before removal
  - Overall comfort
  - Vision
  - [REDACTED]
  - [REDACTED]
  - [REDACTED]
  - Ocular redness
  - [REDACTED]
  - [REDACTED]
  - [REDACTED]
7. [REDACTED]

- [REDACTED]
- [REDACTED]
- [REDACTED]
- [REDACTED]
- [REDACTED]
- [REDACTED]
- [REDACTED]
- [REDACTED]
- [REDACTED]
- [REDACTED]
- [REDACTED]
- [REDACTED]
- [REDACTED]
- [REDACTED]

8. [REDACTED]

9. [REDACTED]

10. [REDACTED]

[REDACTED]

[REDACTED]

11. [REDACTED]

[REDACTED]

12. The investigator will then conduct a complete biomicroscopic examination as detailed in section 3.2.1.

13. The second randomised lens pair will be fitted and allowed to settle for five minutes. The subject will be masked to the lenses.

14. The same procedures as for Dispensing 1 (3.2.1) points 8-14 will be carried out.

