### Study summary

This subject-masked, randomised, bilateral crossover study will compare the clinical performance and subjective acceptance of the clariti 1day soft contact lens with the DAILIES AquaComfort Plus lens when used on a daily wear, daily disposable basis.

Seventy subjects will be enrolled on this study and will wear each lens brand for one week in random sequence. The following will be assessed throughout the study: ocular physiology, [redacted] ocular redness, [redacted] and subjective response.

A study summary is shown in Table 1.

Visit	Procedures
Information presentation Dispensing 1	Short one presentation of study aims and procedures Informed consent taken Explanation of study procedures and subject instructions Ocular and contact lens history [redacted] Autokeratometry Ocular redness assessment Biomicroscopy Fitting of study lens pair 1 [redacted] Subjective scores Issue study lenses and diary
Follow-up 1 / Dispensing 2	[redacted] [redacted] [redacted] Removal of lens pair 1 [redacted] Ocular redness assessment Biomicroscopy Fitting of study lens pair 2 [redacted] [redacted] [redacted]
Follow-up 2	[redacted] [redacted] [redacted] Removal of lens pair 2 [redacted] Ocular redness assessment Biomicroscopy [redacted] Exit form signed [redacted]

Table 1: Study summary.

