### 1.5 Statistical considerations

The principal hypothesis to be tested in this work is that biomicroscopic and subjective scores for the lenses will be substantially equivalent.

[REDACTED] biomicroscopy, ocular redness, [REDACTED] and subjective responses will generate data that are likely to be continuous and normally distributed. As such, these will be compared using linear regression models or other parametric methods. Subjective preferences will be compared using chi-squared tests.

[REDACTED]  
Deviations from this statistical plan will be discussed in the final report. Deviations may be necessary due to differences between the actual data distribution compared with the anticipated data distribution.

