### 3.2 Visit conduct

#### 3.2.1 Pre-enrolment

Prior to the dispensing visit, each subject will be asked to watch a short on-line information presentation detailing study visits and procedures. They will be asked to complete several multiple-choice questions to gauge their understanding of the study. Upon successful completion of these questions, the subject will be booked to attend the Dispensing 1 visit. *Subjects should be asked to attend this visit not having worn their habitual contact lenses on the day of the visit.*

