7. The first randomised lens pair will be fitted and allowed to settle for five minutes. The subject will be masked to the lens brand.

8. [REDACTED]

9. [REDACTED]

10. [REDACTED]
11. The subject will be asked to score the following subjective scores with reference to appropriate vertical visual analogue scales (0-100) [REDACTED]
  - Comfort
  - Vision
  - Overall score

12. [REDACTED]

Subjects will [REDACTED] be given a supply of contact lenses which will be over-labelled to maintain masking, for the first study period.

13. [REDACTED]  
[REDACTED]  
[REDACTED]  
[REDACTED]

14. The subject will then be discharged and asked to return for the one-week follow-up visit wearing the study lenses for at least two hours. Subjects should be asked to wear their lenses for a minimum of eight hours per day, five days per week.

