**3.2.4 Follow-up 2 visit**

*Subjects should attend wearing the study lenses which should have been in situ for at least two hours. Subjects who attend without lenses in situ for at least two hours will usually be rescheduled.*

1. The same procedures as at Follow-up 1 (3.2.2) points 1-12 will be carried out.

2. [REDACTED]  
[REDACTED]  
[REDACTED]
3. The subject will then be unmasked to the study lens types and the order of wear.  
[REDACTED]  
[REDACTED]  
[REDACTED]
4. At the final visit (or when the subject is discontinued at an earlier visit) the subject will sign a study exit statement acknowledging that the work is complete, although they may have been asked by the investigator to attend a post-study follow-up visit, and that they should continue to use their lenses and solutions as advised, and seek aftercare for their contact lenses. A copy of this signed form will be issued to the subject.
5. The subject will be issued with their payment and discharged.

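### Dispensing scores start from different eye states in the two periods; committing to a period term in the analysis would be a cheap gain in precision

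*Combined protocol and SAP*

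**What the plan says.** **First fitting.** Section 3.2.1 (Pre-enrolment) states: "Subjects should be asked to attend this visit not having worn their habitual contact lenses on the day of the visit". In 3.2.2 (Dispensing 1), after biomicroscopy, "The first randomised lens pair will be fitted and allowed to settle for five minutes". Item 11 then collects comfort, vision and overall score on 0–100 scales.

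**Second fitting.** Section 3.2.3 (Follow-up 1) states: "Subjects should attend wearing the study lenses which should have been in situ for at least two hours". Table 1 in the Study summary lists "Removal of lens pair 1" at this visit, before biomicroscopy. Then "The second randomised lens pair will be fitted and allowed to settle for five minutes", and "The same procedures as for Dispensing 1 (3.2.1) points 8-14 will be carried out", which brings in the item 11 scores again. The section number in that cross-reference is off by one (Dispensing 1 is 3.2.2), but the intent is clear.

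**One-week scores.** Section 3.2.4 (Follow-up 2) states: "The same procedures as at Follow-up 1 (3.2.2) points 1-12 will be carried out". It repeats the two-hour wear requirement, so the one-week scores are taken under matching conditions.

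**Analysis.** Of the continuous measures, 1.5 says: "As such, these will be compared using linear regression models or other parametric methods". Section 1.5.1 lists comfort at lens dispensing among the measures with power of 0.8 or more at 65 completing subjects, on a two-tailed paired basis with alpha 0.05. Sections 1.4 and 2.7 randomise the order; no balancing method is visible. Parts of 1.5, the appendices and several items of 3.2.3 between the scoring and the second fitting are redacted.

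**The concern.** The dispensing scores are not taken from the same starting point in both periods. Before pair 1 the eye has had no lens that day. Before pair 2 it has had at least two hours of lens 1 that day, after about a week on that lens. If this moves a score taken soon after fitting, every subject carries a period effect, whichever lens comes first.

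A plain paired test would comply with the visible wording. It leaves the period effect in the error term, because the effect adds to the lens difference in one sequence and subtracts from it in the other. The interval for the lens difference is then wider than it needs to be. That matters here because the principal hypothesis is substantial equivalence of the lenses, which is best supported by a narrow interval. If chance makes the sequences unequal, the lens estimate is also shifted by a fraction of the period effect.

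**Working it through.** **Inputs from the plan (1.5.1).** 65 completers, two-sided alpha 0.05, paired analysis, power 0.8 or greater. No effect size or SD is visible, so the stated power cannot be reproduced. It can only be inverted.

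**Assumed.** k is the period effect (period 1 minus period 2) in units of the within-sequence SD of the paired difference. The documents give no value, so a range is shown. Sequence splits are also assumed.

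**Step 1: implied lens effect.** Power 0.80 from a noncentral t with 64 df gives d = 0.353 SD (noncentrality 0.3528 × √65 = 2.845).

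**Step 2: model.** The A − B difference has mean d + k in sequence AB and d − k in sequence BA, with SD 1 within sequence.

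**Step 3: with a period term.** The lens effect is the average of the two sequence means, with SE = ½√(1/n₁ + 1/n₂) and 63 df. The result does not depend on k.
- 33/32: SE 0.1240, noncentrality 2.844, power 0.7997.
- 39/26: SE 0.1266, noncentrality 2.787, power 0.784.

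**Step 4: plain paired test, interval width.** Its expected variance is 1 + k²·(4n₁n₂/n)/(n − 1). At 33/32 the multiplier of k² is (4 × 33 × 32/65)/64 = 1.015. The width ratio to the adjusted interval is about √(1 + 1.015k²).

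**Step 5: plain paired test, power and type I error (simulation).** In the 33/32 column the extra subject is in the sequence where the period effect adds to the lens difference; in the 32/33 column it is in the other.

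| k | Power 33/32 | Power 32/33 | CI width ratio | Type I error, 33/32 | Type I error, given 39/26 |
|---|---|---|---|---|---|
| 0.25 | 0.79 | 0.77 | 1.03 | 0.043 | 0.06 |
| 0.5 | 0.75 | 0.71 | 1.12 | 0.029 | 0.08 |
| 1.0 | 0.56 | 0.46 | 1.42 | 0.006 | 0.12 |

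The k = 1.0 row is an extreme: a period effect nearly three times the detectable lens difference (1/0.353 = 2.8).

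**Step 6: level over the randomisation.** Averaged over simple randomisation of 65 subjects, the plain test's type I error is 0.050 to 0.051 for k from 0.25 to 1.0. A split of 39/26 or worse has probability 0.14 (binomial, 65, ½). Given that split, the estimate shifts by k × (39 − 26)/65 = 0.2k.

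**Step 7: if the previous study's SD already contains the period effect.** The lens effect is then 0.353 × √(1 + k²). For k = 0.25, 0.5 and 1.0 the plain test has power 0.81, 0.84 and 0.90 at 33/32, or 0.80, 0.81 and 0.85 at 32/33. With a period term it is 0.82, 0.88 and 0.98.

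**The case against.** - **Redaction.** Text is blacked out in 1.5, exactly where a period term would be named, and in 3.2.3 between the scoring and the second fitting, where a lens-free interval might be stated. This stands: the point shows only that neither is visible.
- **The wording already permits the term.** Linear regression is named first, and a power calculation on a paired basis is not an analysis model. This also stands, so the point asks for a commitment and does not allege a contradiction.
- **The starting states share a good deal.** Both fittings follow biomicroscopy with fluorescein, both allow five minutes to settle, and all subjects are current or recent soft lens wearers. What visibly differs is same-day wear and the preceding week on a study lens. Nothing in the documents shows that this changes an early comfort score.
- **The size is assumed.** At k = 0.25 near balance the loss is only 0.01 to 0.03 in power. Because 1.5.1 gives 0.8 as a floor over a list of measures, dispensing comfort may be above it.

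A reader might infer from the last column of the table that the planned comparison is biased or has an inflated error rate. The documents do not support that. Order is randomised, so expected bias is zero; the level averages to 0.05 under simple randomisation, and near balance the plain test is conservative. The rise to 0.06–0.12 is conditional on an uneven split such as 39/26, under a randomisation method the documents do not state.

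**Conclusion.** The point holds as a cheap improvement, not as an error. The schedule builds a different starting state into a powered measure, and the visible analysis does not commit to the term that would account for it. The gain is precision, plus protection if the realised sequences are uneven. Near balance, power set at 0.80 falls to 0.77–0.79 at k = 0.25 and 0.71–0.75 at k = 0.5 without the term, with intervals about 3% and 12% wider.

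These figures rest on assumed values of k, on 65 completers and on a true power of exactly 0.80. If the previous study's SD already includes a comparable period effect, the stated 0.80 is still essentially met and the term is pure gain. It would therefore be wrong to conclude that the trial is underpowered. The point concerns the dispensing scores; for the one-week scores, taken under matching conditions, a period term is a routine safeguard.

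**What to change.** Add to 1.5:

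> Subjective scores with one value per subject per lens, including comfort, vision and overall score at dispensing, will be analysed with lens and period as fixed effects and subject as a random effect, and the lens difference reported with its 95% confidence interval.

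The restriction to one value per subject per lens is deliberate. Biomicroscopy is recorded for each eye, and a model with subject as the only random effect would ignore the extra correlation between eyes of one subject in the same lens. If the model is extended to those scores, average the two eyes or add a within-subject eye structure.

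The cost is one sentence and one degree of freedom (64 to 63). With no period effect at all, power goes from 0.800 to 0.7997 at 33/32 and to 0.784 at 39/26. Visits, procedures and sample size are unchanged. The term does not remove carry-over specific to one lens. If the redacted text already includes it, no change is needed.

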**3.2.4 Follow-up 2 visit**

*Subjects should attend wearing the study lenses which should have been in situ for at least two hours. Subjects who attend without lenses in situ for at least two hours will usually be rescheduled.*

1. The same procedures as at Follow-up 1 (3.2.2) points 1-12 will be carried out.

2. [REDACTED]  
[REDACTED]  
[REDACTED]
3. The subject will then be unmasked to the study lens types and the order of wear.  
[REDACTED]  
[REDACTED]  
[REDACTED]
4. At the final visit (or when the subject is discontinued at an earlier visit) the subject will sign a study exit statement acknowledging that the work is complete, although they may have been asked by the investigator to attend a post-study follow-up visit, and that they should continue to use their lenses and solutions as advised, and seek aftercare for their contact lenses. A copy of this signed form will be issued to the subject.
5. The subject will be issued with their payment and discharged.

### **3.2.5 Post-study follow-up visit**

In the case of a subject who exits the study with significant clinical signs or symptoms, the investigator must undertake to examine the subject at intervals he/she determines to be clinically appropriate until the sign or symptom has resolved or returned to a level that is considered to be clinically acceptable. Details from these visits will be recorded on a post-study follow-up visit form.

### **3.3 Monitoring subject compliance**

Subjects are required to adhere to the instructions provided during this clinical investigation. This will be confirmed at the study visits by verbal questioning of the subject by the investigator.

### **3.4 Missing, unused and spurious data**

The absence of any data will be carefully and critically considered. If appropriate, partial datasets will be included in the final analysis. Any data missing from a subject visit will be outlined in the report by indicating the number of subjects included for each analysis. Data that are unused or considered to be spurious will be detailed and discussed in the report.

## Section 4. Study co-ordination

### 4.1 Document processing

All case report forms will be processed and evaluated by Eurolens Research, who will produce the final report with full statistical analysis. A draft report will be sent to the Industrial Contact Person in order to make comments and ask for re-drafts. If no comments are received from the Industrial Contact Person within eight weeks, a final report will be released with a separate document control page (in duplicate), requesting the Industrial Contact Person to sign both copies, one to keep and the other to be returned to Eurolens Research.

